APPENDIX 1. EXAMPLE OF SCHEDULE OF STUDY VISITS

	VISIT 1 (Day/Week/Month #) ^a	VISIT 2 (Day/Week/Month #) ^a	VISIT 3 (Day/Week/Month #) ^a	VISIT 4 (Day/Week/Month #) ^a	VISIT 5 (Day/Week/Month #)
Informed Consent	X				
Medical History	X				
Complete Physical Exam	X				X
Abbreviated Physical Exam		X	X	X	
Height	X	X	X	X	X
Weight	X	X	X	X	X
Randomization	X				
Quality of Health Survey ^b	X		X		X
Initiate Subject Diary	X				
Subject Diary Review		X	X	X	X
Adverse Experiences	X	X	X	X	X

^a ±2 day

^b The Quality of Health Survey may be administered over the phone or email if needed.

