1 BACKGROUND AND OVERVIEW OF CLINICAL STUDIES

Increasing physical activity levels may improve cardiovascular health and BP levels in young individuals, especially if such strategies promote healthy lifestyles. Physical activity is currently recommended for adults CV health, but physical activity levels are known to be low in populations with diabetes or chronic kidney disease.^{5,6,7,8} One prior study of the use of pedometers (not associated with wireless technology or provider feedback) in children with CKD did not significantly improve physical activity levels.⁹ Supervised walking appeared to provide some benefit in individuals with type II diabetes, but overall compliance was poor.^{9,10} Interview of adolescents and young adults with chronic illnesses has shown preference for the use of electronic devices and online tools for disease management.^{11,12} Thus, use of sophisticated electronic devices such as FitBits[©] (wireless pedometers worn on the wrist that sync with cell phones) may improve disease control by engaging young patients in self-monitoring of their own health and lifestyle behaviors. FitBits[©] have been previously validated in clinical studies for the accuracy of step count.¹³

PROTOCOL SYNOPSIS

TITLE	Physical Activity Trackers to Blood Pressure (PAT-BP)
SPONSOR	NIH
FUNDING ORGANIZATION	NHLBI
NUMBER OF SITES	1
RATIONALE	The rationale for this study is to determine whether use of physical activity trackers (Fitbits) helps improving patient self-awareness of their fitness level and enhance healthy lifestyle changes that may lead to lower blood pressure. The potential benefits (increased walking on a daily basis and awareness of own fitness level) outweigh the risks in this study (anxiety about step count, minimal risk of loss of confidentiality).

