STUDY DESIGN	
This is a pilot randomized controlled trial.
 
We will recruit 75 adolescents and young adults at UCSF. Patients included for study will be between ages 8-30 receiving anti-hypertensive therapy at the time of recruitment or have elevated BP > 120 mm Hg or > 95th percentile for age/sex/height if < 18 years of age.^{14,15}
 
Study intervention. Daily use of physical activity tracker coupled with biweekly provider telemonitoring and feedback (via secure email, phone call, or text) will be compared to usual care (daily use of physical activity tracker with biweekly feedback for the latter 6 months of the study). The study intervention will last 6 months for patients in the usual care group and 12 months for patients in the intervention group. Physical activity and data will be reviewed by telemonitoring on a biweekly basis by study personnel. Patients will receive feedback on their progress from study personnel via patient-preferred communication modalities (secure e-mail, phone call, or text) biweekly. If daily step count is below desired goal (as per age-appropriate references),¹⁶ patients will be provided with ideas on how to increase physical activity level/step counts (e.g. parking further from their destination and walking, taking stairs instead of elevator).

OBJECTIVES	
To determine feasibility of a randomized controlled trial testing to effect of physical activity trackers on blood pressure levels.
 
To determine potential effect sizes from the use of physical activity trackers on change in blood pressure.

NUMBER OF SUBJECTS	75

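### Does the lack of a named record of anti-hypertensive drug changes undermine the pilot blood pressure estimate?

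*Combined protocol and SAP*

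**What the plan says.** Anti-hypertensive treatment appears only as a condition of entry. The synopsis (Study Design) admits patients "receiving anti-hypertensive therapy at the time of recruitment or have elevated BP > 120 mm Hg" or above an age-specific percentile; the Subject Selection Criteria mention only those on therapy. No text asks for drug treatment to be held constant, and usual care is routine clinical care for the first six months.

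Appendix 1 is titled "APPENDIX 1. EXAMPLE OF SCHEDULE OF STUDY VISITS". The rows that might hold drug information are "Medical History" (Visit 1 only), "Subject Diary Review" (Visits 2 to 5) and "Adverse Experiences" (all visits). The content of none of them is defined.

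The second objective is "To determine potential effect sizes from the use of physical activity trackers on change in blood pressure". The Rationale expects the tracker to "enhance healthy lifestyle changes that may lead to lower blood pressure". The Primary Analysis Plan describes feasibility outcomes first. It then compares change in office systolic BP from 3 to 12 months by intention to treat, with t-tests and mixed models containing a time-by-arm term. It mentions no summary of medication.

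**The concern.** Drug treatment acts directly on the measured outcome. Starts, stops and dose changes are foreseeable over 12 months in people treated for hypertension or with raised BP. Patients and investigators know the arm, and for the first six months only the intervention arm receives "Daily use of physical activity tracker coupled with biweekly provider telemonitoring and feedback". If drug changes were more common in one arm, part of any BP difference could come from drugs rather than activity, and a null result could hide an activity effect offset by drug changes. The data named in the plan could not show this. The pilot's effect size might then be carried into a larger trial as a tracker effect when it was partly something else. Dates and doses not collected during the trial may also be hard to recover later.

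**Working it through.** **1. Is the absence real?** Yes. Across the background, synopsis, analysis plan and appendix, no text names a record of drug, dose or date of change, or a by-arm summary.

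**2. What does the absence show?** Appendix 1 still carries unfilled day/week/month placeholders in its column heads. It has no row for BP, although office BP is analysed, and none for tracker data, although Study Design describes biweekly review of it. A schedule silent on the trial's own outcome and intervention is not a list of what is collected. The history and diary rows could hold drug data. This is missing detail, not a decision to leave drugs out.

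**3. Does the document give a reason to expect unequal drug changes?** Only weakly. Study Design describes the biweekly contact as review of activity data by study personnel, feedback on progress and, when step counts are low, ideas for walking more. It mentions no BP review, prescribing or drug advice. Usual care receives the tracker and feedback from month 6, so within the 3-to-12-month contrast the difference in contact covers months 3 to 6, which is 3 of 9 months.

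**4. How large could the effect be?** The document supplies only N (up to 75) and the 2:1 ratio, hence 50 and 25 if all are enrolled. The SD of BP change, the drug effect and the arm gap are assumptions. There is no figure in the plan to reproduce.

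Half-width of the 95% interval = t(0.975, 73) × SD × √(1/50 + 1/25) = 1.993 × 0.2449 × SD = 0.488 × SD.

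| SD of change (assumed) | Half-width, mm Hg |
|---|---|
| 10 | 4.88 |
| 12 | 5.86 |
| 15 | 7.32 |

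Shift in the BP difference = arm gap in the share with a net drug change × mm Hg per change (6 to 10 assumed).

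| Arm gap | Shift, mm Hg | Share of half-width at SD 12 |
|---|---|---|
| 10 points | 0.6 to 1.0 | 10 to 17% |
| 20 points | 1.2 to 2.0 | 20 to 34% |
| 30 points | 1.8 to 3.0 | 31 to 51% |

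Over all three SDs the share runs from 0.6/7.32 = 8% to 3.0/4.88 = 61%. The direction is unknown. Every shift is smaller than the half-width, and dropout would widen the interval further.

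**5. What would a by-arm table of drug changes add?** Suppose the true rate of drug change is the same in both arms. Exact binomial probabilities of an observed gap at 50:25 are:

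| True rate | Gap of 10 points or more | Gap of 20 points or more |
|---|---|---|
| 10% | 0.217 | 0.010 |
| 20% | 0.358 | 0.052 |
| 30% | 0.424 | 0.090 |
| 40% | 0.455 | 0.113 |

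So a 10-point gap appears by chance 22 to 45% of the time. A two-sided Fisher test at 0.05 would detect a true 10-point gap (10% vs 20%, or 20% vs 30%) with power of only about 0.12 to 0.18. For a true 20-point gap (10% vs 30%, or 20% vs 40%) the power is 0.38 to 0.51. The table could flag a large imbalance but could not interpret a modest one.

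**6. Would the table change the estimate?** No. Drug changes after randomisation may follow from assignment, for instance a reduction once BP has fallen. They are part of the intention-to-treat effect, and a descriptive count cannot divide that effect into an activity part and a drug part.

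**The case for a change.** The best case for a change is that it costs little: some data entry at existing visits and one table. Effect size is one of only two stated objectives. Sampling error is visible in the confidence interval, whereas an unrecorded drug imbalance is visible nowhere, so a shift smaller than the half-width is not thereby harmless. BP, though also missing from the schedule, is at least named in the analysis plan; drug changes are named nowhere. Diary content left undefined does not guarantee the same information from both arms.

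Much of this stands. Recording drugs and doses is good practice, and a reader of the pilot result would welcome the context. What does not stand is the step to a needed amendment. The BP contrast is valid without the table, and the table would not resolve the attribution question said to be at stake. Attribution is limited more directly by a feature the plan states openly: usual care wears the tracker from month 6, inside the 3-to-12-month contrast. Drug records would not remove that limit.

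**Conclusion.** No change to the plan is called for. The plan does leave unsaid where drug changes are recorded, but this is a lack of detail in a short pilot document with a template schedule. Analysts can fill it sensibly from the history, diary or clinical record when they describe the cohort. The randomised BP comparison and its test are unaffected. The plausible shift of 0.6 to 3.0 mm Hg rests wholly on assumed drug effects and arm gaps. It is smaller than the 4.9 to 7.3 mm Hg half-width expected with 75 patients fully followed and an SD of 10 to 15. The document describes the extra contact as activity feedback only, so it shows no clear route to unequal prescribing. The pilot BP estimate should be read as the effect of being assigned to the programme, including any drug changes that followed from it. This conclusion would weaken if the BP difference were to be presented as a pure activity effect, or if study contacts in practice included BP or drug advice.
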